6.3. Statistical Analysis: Statistical Analysis Plan

Protocol	Assessment of the effect of lifestyle intervention plus water-soluble cinnamon extract on lowering blood glucose in pre-diabetics: A randomized, double-blind, multicenter, placebo controlled TRIAL.
Principal Investigator(s)	Lt Col [name], USAF, MC 99 th MDG
Statistical Analysis Plan	[name], Ctr AFMSA/SG5M South
Statistical Analysis	[name], Ctr AFMSA/SG5M South

Technical Objective: The objective of this study is to compare Cinnulin PF, a cinnamon extract, in combination with a lifestyle management program, to a placebo and life style management program, and to evaluate the prevention or delay the development of Type 2 diabetes in persons with pre-diabetes.

Sample: Subjects will be a random sample of males and females between the ages of 18-65 years with a diagnosis of pre-diabetes seen in certain Air Force medical treatment facilities. The subjects are presumed to be randomly selected from the population of patients obtaining similar care at all Air Force medical treatment facilities.

Hypothesis:

H₀₁ – No difference in means of continuous dependent variables between and among treatment groups
H₀₂ – Cinnulin + Life Style and Placebo + Life Style groups have identical survival functions for the time to reach the Type 2 diabetes conversion event.

Study Design: The experimental design of this study is a mixed effects, randomized complete block design with repeated measures. Subject is a random effect as the subjects are a sample randomly selected and randomly assigned to a treatment group. Fixed effects are treatment group and time of repeated measure as these effects cannot be generalized to other treatments and times. Subjects will be randomly assigned to each treatment group.

Factors:

1. Subject
2. Treatment: Cinnulin PF + Life Style Management versus Placebo + Lifestyle Management
3. Repeated Measurements: Laboratory and physical measurements obtained from each subject at fixed intervals for the duration of the study (N=8).

¹ Faul F, Erdfelder E, Lang A-G, Buchner A. G*Power 3: A flexible statistical power analysis program for the social, behavioral, and biomedical sciences. *Behavior Research Methods*. 2007; 39 (2): 175-191.

² Glantz SA. *Primer of Biostatistics*. McGraw-Hill, 2002, 438-440.

Outcome Variables:

1. Diabetic indicators
 - a. Glucose
 - b. Hemoglobin A1c
 - c. Lipid panel (cholesterol, triglycerides, HDL, LDL)
 - d. Waist circumference
2. Type 2 diabetes conversion: Yes/No

Other Variables of Interest among Subjects

1. Subject Demographics
 - a. Age (years)
 - b. Marital Status (single versus married)
 - c. Gender
 - d. Race/Ethnicity (African American, European American, or Hispanic, 2 parameters)
 - e. Specialty codes (categorized into office work, logistics, or combat specialties, 2 parameters)
 - f. Military Grade (Officer grades categorized into company, field or higher ranks; enlisted into E1 – E6 or E7 – E9).

Sample Size Estimation and Power Analysis: A priori power for H_01 was assessed using G*Power Version 3.0.10³. The results shown below indicate 214 subjects per group with 8 repeated measures for a total sample size of 3424 will achieve a power of approximately 0.99 to detect a small effect size of 0.10 at $\alpha = 0.0004$.

Input:	Effect size f	=	0.1
	β/α ratio	=	4
	Total sample size	=	3424
	Number of groups	=	2
	Repetitions	=	8
	Corr among rep measures	=	0.8
Output:	Noncentrality parameter λ	=	41.503030
	Critical F	=	12.389225
	Numerator df	=	1.000000
	Denominator df	=	3422
	α err prob	=	0.000437447
	β err prob	=	0.00174979
	Power (1- β err prob)	=	0.998250

[figure not shown]

Figure 1. rANOVA Power, $\beta = 0.002$, $\alpha = 0.0004$, 214 subjects per group

Post hoc analyses to evaluate differences within clinically significant time intervals will be tested with one-tailed t-tests for independent samples. The power analysis, using G*Power Version 3.0.10⁴, is shown below and shows 214 subjects per group will achieve a power of approximately 0.85 to detect a small effect size of 0.20. To lessen the probability of a false negative, a β/α ratio of 1 was employed.

t tests - Means: Difference between two independent means (two groups)

Analysis:	Compromise: Compute implied α & power		
Input:	Tail(s)	=	One
	Effect size d	=	0.2
	β/α ratio	=	1
	Sample size group 1	=	214
	Sample size group 2	=	214
Output:	Noncentrality parameter δ	=	2.068816
	Critical t	=	1.035015
	Df	=	426
	α err prob	=	0.150624
	β err prob	=	0.150624
	Power (1- β err prob)	=	0.849376

³ Faul F, Erdfelder E, Lang A-G, Buchner A. G*Power 3: A flexible statistical power analysis program for the social, behavioral, and biomedical sciences. *Behavior Research Methods*. 2007; 39 (2): 175-191.

⁴ Ibid.

[figure not shown]

Figure 2. *t*-test Power, $\beta = 0.15$, $\alpha = 0.15$, 214 subjects per group

A priori power for H_02 was assessed using the method described by Glantz⁵ to calculate sample size for a two-sample log-rank test to detect differences in the time to event. Based on this design, it will require a minimum of 214 subjects per group to detect a difference between a 17.5% conversion in the placebo + lifestyle and an 11.5% conversion in the cinnulin + lifestyle group at $\alpha = 0.05$ (one-sided) and power of 0.80.

Power Analysis Log-Rank Test for Two Samples	
α	0.050
$Z_{.05(2)}$	1.64
$1-\beta$	0.80
$Z_{.80(\text{upper})}$	-0.842
$S_2(\infty)$	0.885
$\text{Ln}S_2(\infty)$	-0.122168
$S_1(\infty)$	0.825
$\text{Ln}S_1(\infty)$	-0.192372
ψ	0.6350597
d (primary endpoint events) =	124
n (sample size to achieve this number of events) =	428
Groups/Treatments	2
Subjects required per group/treatment	214

Steps of Analysis

Descriptive statistics: Sample means and standard errors of measurement of interval variables will be calculated, and frequency distributions of nominal variables will be calculated and graphed for the total sample and for the Cinnulin/Lifestyle Management groups. Homogeneity of the groups will be tested with a two-tailed *t*-test and two-tailed Fisher's exact test for interval and nominal variables respectively.

Hypothesis Testing

H_01 – This hypothesis will be tested by a mixed effects repeated measures analysis of variance (rANOVA).

H_02 – This hypothesis will be tested by developing Kaplan-Meier survival curves and survival functions compared with a log-rank test.

Post Hoc Tests: In the event H_01 is rejected, contrasts will be used to investigate effects and differences within clinically significant time intervals. In the event multiple univariate tests are used to investigate effects, the Bonferroni⁶ or Holm's method⁷ will be used to correct the level of significance for multiple comparisons.

Analysis Tools:

SAS Version 9.2 for Windows (SAS Institute, Cary, North Carolina)

R Version 2.13.1 (R Foundation for Statistical Computing)

Microsoft Excel (Microsoft Corporation, Seattle, Washington)

6.4 Number of Subjects:

Number of subjects recruited at WHASC	46
---------------------------------------	----

⁵ Glantz SA. *Primer of Biostatistics*. McGraw-Hill, 2002, 438-440.

⁶ Abdi H. Bonferroni and Šidák. Corrections for multiple comparisons. In N.J. Salkind (ed.). *Encyclopedia of Measurement and Statistics*. 2007; Thousand Oaks, CA: Sage.

⁷ Holm, S. 1979. A simple sequential rejective multiple test procedure. *Scand. J. Statistics*, 6: 65-70.

Number of subjects recruited at Nellis AFB	106
Number of subjects recruited at DGMC	76
Number of subjects recruited atEglin (actual)	53
Numerb of subject recruited at Offutt	2

TOTAL NUMBER OF SUBJECTS: 557 (nation-wide/study-wide): **428** (completing the study)

7. Duration of Study: Approximate duration of the study: 6 years

8. Intramural Funding/Local Support Services Required:

We received a grant for Intramural funding from the AFMSA/SG9S in the amount of approximately \$639,036.36. We received a second grant from the 59MDW/ST for approximately \$618,000 over 2 years. This is to support the salaries of four Medical Assistants, costs associated with Group Lifestyle Balance training, and site monitoring visits.

9. Extramural Funding/External Support Services Required:

Integrity Nutraceuticals, Inc. will provide Cinnulin PF and placebo to Geneva Research Foundation who will administer the grant. Collaborating Institution Support: This study will be sponsored by Integrity Nutraceuticals, Inc. The collaborative research will be executed in accordance with 15 USC 3710a through a Cooperative Research and Development Agreement, (pending approval) between the 99th MDG and Integrity Nutraceuticals, Inc. Integrity Nutraceuticals, Inc. shall provide the Air Force activity: 1 gram (2-500 mg capsules) Cinnulin PF tablets for approximately 279 subjects taking once a day for 1 year (\$280,370.00) and Placebo pills for approximately 279 subjects taking once a day for 1 year (\$1,870.00) to include shipping costs to the Air Force Activity. The estimated fair market value of the support is \$282,240.00.

10. Financial Conflict of Interest: No financial conflicts of interest exist.

11. Use of an Investigational New Drug, use of a Drug for a non-FDA approved purpose, use of an investigative device or use of a placebo:

This research uses an Investigational New Drug YES NO
This research uses a FDA approved drug for a non-FDA approved purpose YES
 NO
This research uses an Investigational Device YES NO
This research uses a placebo. YES
 NO

12. Medical Research Area for the Study: (Pick as many as appropriate)

 Analytical Chemistry	 Anatomy	 Anesthesiology	 Biochemistry
 Cardiovascular Surgery	 Cardiology	 Cell Biology	 Dentistry
 Dermatology	 Dietetics	 Electrophysiology	 Endocrinology
 Emergency medicine	 Gastroenterology	 General Surgery	 Hematology
 Histology	 Immunology/Allergy	 Infectious Disease	 Microbiology
 Molecular Biology	 Neonatology	 Neurology	 Neurosurgery
 Nursing	 OB/GYN	 Occupational Medicine	 Occupational Therapy
 Oncology	 Ophthalmology	 Oral/Maxillofacial Surgery	 Orthopedics
 Pathology	 Pediatrics	 Pharmacology	 Physical Therapy
 Mental Health	 Radiology/Imaging	 Urology	 Wellness
 Other (state): Family Medicine, Internal Medicine, Family Health Clinic			

13. Attachments:

1. Study Medication Diary
2. Certificate of Compliance
3. Informed Consent Document
4. HIPAA Authorization Form
5. Placebo justification
6. Advertisement flyer
7. Letter for Mailing
8. Travis AFB Advertisement Flyer
9. Investigational New Drug Worksheet
10. H33-Local and External Support Document
11. H32 Intramural and Extramural Funding Support Document
12. RAND 36-Item Health Questionnaire
13. Form A2-Study Personnel
14. Medication Disposal

15. Algorithm for Determining Whether an Adverse Event is an Unanticipated Problem
16. Form J HIPAA Waiver or Alteration

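### As written, the H01 model implies equal correlation between all 8 visits; if correlation falls with time, contrasts between time intervals get wrong standard errors, while the main effect does not

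*Combined protocol and SAP*

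**What the plan says.** All of this is in section 6.3, the Statistical Analysis Plan.

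- Study Design describes the trial thus: "The experimental design of this study is a mixed effects, randomized complete block design with repeated measures". On the random part it says "Subject is a random effect as the subjects are a sample randomly selected and randomly assigned to a treatment group". On the fixed part it says "Fixed effects are treatment group and time of repeated measure as these effects cannot be generalized to other treatments and times". No treatment-by-time term is listed.
- Hypothesis Testing assigns H01 to a mixed effects repeated-measures ANOVA. No residual covariance structure, sphericity test, Greenhouse-Geisser-type correction or robust variance is named there or elsewhere.
- Factors gives 8 repeated measurements. The power input is one common value: "Corr among rep measures = 0.8".
- Post Hoc Tests says that, once H01 is rejected, "contrasts will be used to investigate effects and differences within clinically significant time intervals", with Bonferroni or Holm if several univariate tests are used.
- Sample Size Estimation and Power Analysis describes the post hoc work differently, as one-sided two-sample t-tests, with an implied alpha of 0.150624.

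**The concern.** A random subject effect with independent residuals is compound symmetry: every pair of visits has the same correlation, and one pooled residual variance serves every within-subject contrast. Under section 3.6, Visits 2 to 9 run from month 3 to month 24 and product stops at month 12. I take these to be the 8 measurements, 4 on product and 4 off. Readings of glucose, HbA1c, lipids and waist 21 months apart may well be less alike than readings 3 months apart. In that case the pooled variance is too small for comparisons of distant visits and too large for neighbouring ones.

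At stake is any claim that the treatment effect changed over time, for example that it faded after product stopped. Such a claim could appear too easily, while a real change between adjacent visits could be missed.

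**Working it through.** **The plan's own figure.** The H01 power output uses the equal-correlation formula for a between-subject effect, λ = f²·N·m / (1 + (m − 1)ρ). With f = 0.1, N = 3424, m = 8 and ρ = 0.8, λ = 0.01 × 3424 × 8 / (1 + 7 × 0.8) = 273.92 / 6.6 = 41.503. Solving for β = 4α gives critical F 12.389, α 0.000437 and power 0.99825, all as printed. This confirms two things: the only correlation in the plan is a single constant, and the powered test is the treatment main effect (numerator df 1). Whether 3424 was the right N to enter is a separate matter.

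**Method.** Let R be the true visit correlation matrix (equal variances, complete data, equal arms) and r̄ its average off-diagonal value. For a contrast c of the group differences, in units of the variance of one visit's group difference:

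- true variance = c′Rc
- random-intercept model variance = (1 − r̄)·Σc² when the weights sum to zero
- two-sided false-positive rate = 2[1 − Φ(1.96·√(model variance / true variance))]

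**Worked case (assumed).** Correlation falls linearly from 0.85 at 3 months to 0.70 at 21 months, a step of 0.025 per visit. The average lag over the 28 pairs is 3, so r̄ = 0.85 − 2 × 0.025 = 0.80, the plan's own value.

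- On- versus off-product (weights ±1/4, Σc² = 0.5): model 0.20 × 0.5 = 0.10. Each four-visit mean has variance [4 + 2(3 × 0.85 + 2 × 0.825 + 0.80)]/16 = 0.875. The average lag between the halves is 4, so their covariance is 0.775. True variance is 2(0.875 − 0.775) = 0.20. The ratio is 0.5, the standard error is 29% too small, and the rate is 16.6%.
- Last versus first visit: model 2 × 0.20 = 0.40; true 2(1 − 0.70) = 0.60; rate 11.0%.
- Adjacent visits: model 0.40; true 2(1 − 0.85) = 0.30; rate 2.4%.
- Group difference averaged over the on-product visits: model (1 + 3 × 0.8)/4 = 0.85; true 0.875; rate 5.3%.
- Group difference at one visit: both variances are 1; rate 5.0%. Main effect: both (1 + 7 × 0.8)/8 = 0.825; rate 5.0%.

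**Range over assumed patterns (nominal two-sided 5%).**

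| Correlation, 3 to 21 months apart | Average | On vs off | Last vs first | Adjacent | On-product average | Main effect |
|---|---|---|---|---|---|---|
| 0.8 constant (plan's input) | 0.80 | 5.0% | 5.0% | 5.0% | 5.0% | 5.0% |
| Linear 0.85 to 0.75 | 0.82 | 13.6% | 9.3% | 3.0% | 5.2% | 5.0% |
| Linear 0.85 to 0.70 | 0.80 | 16.6% | 11.0% | 2.4% | 5.3% | 5.0% |
| Linear 0.88 to 0.64 | 0.80 | 22.4% | 14.4% | 1.1% | 5.5% | 5.0% |
| AR(1), 0.9 | 0.74 | 28.3% | 16.7% | 0.2% | 6.1% | 5.0% |

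With an unstructured covariance every entry is 5.0% in large samples, whatever the true pattern.

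**The case against.** A reader might infer that the plan forces compound symmetry and so runs its post hoc tests at up to 28% where 5% was promised. The documents do not support that.

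- **Not forced.** Another residual structure is not excluded. Equal correlation is what the text yields if fitted as it stands.
- **Decay is assumed.** No correlation by time apart is given, and under the plan's own 0.8 nothing is inflated. The 28% comes from a pattern averaging 0.74. An AR(1) pattern rescaled to average 0.8 (parameter 0.9256) gives 28.9%, so the steepness of decay matters more than the average, and the steepness is unknown.
- **The contrast matters.** The plan speaks of differences within intervals. Read as group differences at a visit or averaged over an interval, the rates are 5-6%. Interval-against-interval contrasts are not excluded, but no on-versus-off or last-versus-first test is named.
- **5% is not the stated post hoc level.** The power section implies 0.15 one-sided, and Post Hoc Tests adds Bonferroni or Holm. This does not remove the distortion. In the worked case, on versus off becomes 23% at one-sided 0.15, and 5.7% at an illustrative 0.05/7 = 0.7%.
- **H01 must be rejected first.** With no true effect and rejection judged on the main effect at 5%, a false on-versus-off claim occurs in about 0.05 × 16.6% = 0.8% of trials in the worked case, and 1.1% and 1.4% in the two steeper ones. If the interaction also counts as rejection, simulation gives 5.5%, 8.2% and 10.7%. The unconditional rates matter mainly when a real, constant effect leads to rejection.
- **The t-tests are immune.** Two-sample t-tests at a visit do not use the model's covariance.

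All of this stands and narrows the point. It does not remove it, because Post Hoc Tests still prescribes contrasts and nothing in the plan protects them. The complete-block label is inaccurate, since each subject receives only one treatment, but that is labelling without numerical effect.

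**Conclusion.** The point holds in conditional form and should be corrected. The stated H01 model, taken literally, assumes equal correlation over 21 months without justification or check. If correlation decays, interval-against-interval contrasts taken from it are wrong in both directions: about 14-28% (on versus off) and 9-17% (last versus first) against 0.2-3% (adjacent), at a nominal two-sided 5% before the H01 condition and any multiplicity correction. These figures rest on the assumed decay patterns, equal variances across visits and complete data. Carry-forward imputation, stated in the protocol summary and section 3.6, would itself alter the visit correlations.

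It would be wrong to infer that the main H01 comparison is invalid. The treatment main effect and single-visit group differences keep 5% under every pattern examined, and on-product averages stay at about 5-6%.

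**What to change.** In section 6.3, under Study Design and Hypothesis Testing:

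- State that treatment is a between-subject factor, with subjects nested in treatment, and drop the complete-block label.
- Include treatment, visit and treatment-by-visit as fixed terms. Without the last, a change in treatment effect between intervals cannot be estimated from the model.
- Specify an unstructured covariance over the 8 visits, fitted by REML with Kenward-Roger degrees of freedom. If it does not converge, use heterogeneous Toeplitz, then a robust sandwich variance.

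Under Post Hoc Tests, name the interval contrasts and take them from this model. Reconcile that paragraph with the one-sided t-tests in the power section, so that one method and one significance level apply.

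The cost is 8 × 9/2 = 36 covariance parameters, modest against 428 expected completers, plus a few SAP sentences and a small amount of code. No new data are needed. If correlation really is constant, little is lost.

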 - o Fasting comprehensive metabolic panel (liver function, renal function, plasma glucose tests) via 1 venipuncture (5-10 mls, approximately 1-2 teaspoons of blood will be drawn)
**Subjects who have had a fasting comprehensive metabolic panel test within the two weeks prior to Visit 1 will not need to have this test repeated.*
 - o Hemoglobin A1c via 1 venipuncture (5-10 mls, approximately 1-2 teaspoons of blood will be drawn)
**Subjects who have had a Hemoglobin A1c test within the two weeks prior to Visit 1 will not need to have this test repeated.*
 - o Lipid panel via 1 venipuncture (5-10 mls, approximately 1-2 teaspoons of blood will be drawn)
**Subjects who have had a lipid panel within the two weeks prior to Visit 1 will not need to have this test repeated.*

Visit 1 (Day 1 within-30 days of Screening Visit*labs must be re-done if greater than 2 weeks from Screening Visit):

- Record: whether subject is taking any statins, fibrates, niacin or bile acid binding agent and, if yes, the name of drug, strength and dose.
- Subjects will complete the RAND 36 Item Health Survey.
- Subjects will be randomized by a non-investigator at the pharmacy. We will use a random-number generator and use blocking to ensure roughly equal sample sizes. Both subjects and investigators will be blinded to the study group assignments. Subjects will be randomized by the pharmacy into one of two groups (research-driven):
 - o Group 1: Will take (by mouth) 2 gelatin capsules that contains 1 gram (2-500 mg capsules) water-soluble cinnamon extract (Cinnulin PF) once a day for 1 year plus 2 years of follow-up plus standard of care aggressive lifestyle therapy.
 - o Group 2: Will take (by mouth) 2 placebo capsules (gelatin capsule filled with wheat bran) once a day for 1 year plus 2 years of follow-up plus standard of care aggressive lifestyle therapy.

- Subjects will be provided a pill container to assist with remembering to take their IP and a bathroom scale to weigh themselves with (if available).
- Subjects will be given a Study Medication Diary and will be instructed to bring it with them to next study visit.
- Subjects will be told to fast for at least 10 hours prior to Visit 2.

Visit 2-Month 3 (90 days after Visit 1):

- Record: Weight (in pounds), waist circumference (in inches), blood pressure, verify current email address , and whether subject is taking any statins, fibrates, niacin or bile acid binding agent and, if yes, the name of drug, strength and dose.

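### The H01 model leaves out each outcome's pre-randomisation value; adding it as a covariate gains precision and needs no new data

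*Combined protocol and SAP*

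**What the plan says.** Section 6.3, Study Design, makes subject a random effect and then states: "Fixed effects are treatment group and time of repeated measure". Under Factors, the repeated measurements are described as "Laboratory and physical measurements obtained from each subject at fixed intervals for the duration of the study (N=8"). Under Hypothesis Testing, H01 is assigned to a mixed effects repeated measures ANOVA. No covariate or change from baseline is mentioned.

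Interval comparisons are described twice. The power section says: "Post hoc analyses to evaluate differences within clinically significant time intervals will be tested with one-tailed t-tests for independent samples". The Post Hoc Tests paragraph says: "In the event H_01 is rejected, contrasts will be used to investigate effects and differences within clinically significant time intervals". Neither description mentions baseline.

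Pre-randomisation values could enter the group comparison under Descriptive statistics ("Homogeneity of the groups will be tested with a two-tailed" t-test for interval variables). That comparison has no stated consequence for H01. The demographic variables are listed as being of interest but are not assigned to a model.

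The baseline data exist. Section 3.6 collects the metabolic panel (including glucose), HbA1c, lipids and waist at screening, and Visit 1 adds that "labs must be re-done if greater than 2 weeks from Screening Visit". Visits 2 to 9 (Months 3 to 24) are eight follow-up visits. The procedure table in 3.6.5 counts nine HbA1c tests and nine lipid panels.

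**The concern.** People differ in glucose, HbA1c, lipids and waist before they start, and in a comparison of follow-up means those differences count as noise. A covariate measured before randomisation removes the part it predicts without biasing the treatment comparison. The plan collects the covariate for every H01 outcome and does not use it.

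The precision is needed. The stated H01 power of 0.998 comes from a run that enters 3424 measurements where the formula takes subjects (a separate point). With 428 subjects the unadjusted main-effect test falls far short of that figure, and baseline adjustment is a remedy that needs no more subjects or visits. Timing also matters: adjustment chosen after unblinding would be a data-driven choice.

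**Working it through.** **Inputs from Section 6.3.** f = 0.10 (d = 0.2 for two equal groups); m = 8; "Corr among rep measures" ρ = 0.8; 214 per group. **Assumed:** correlation r between baseline and each follow-up value, from 0 to 0.8, the same at every visit; complete data unless stated.

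**1. The plan's own figure.** λ = f² × N × m / (1 + (m−1)ρ) = 0.01 × 3424 × 8 / 6.6 = 41.503. With β/α = 4 this gives critical F 12.389, α 0.000437 and power 0.99825, as stated. One numerator degree of freedom makes it the between-group main effect. Since 3424 = 428 × 8, the subject-based value is λ = 0.01 × 428 × 8 / 6.6 = 5.19.

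**2. Effect of the covariate on the 8-visit mean.** In units of σ², the variance of a subject's mean is V = (1 + 7 × 0.8)/8 = 0.825. With baseline as a covariate it is 0.825 − r². Then λ = d² × (N/4)/variance = 4.28/variance for N = 428, on 1 and 426 df unadjusted or 425 adjusted.

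| r | variance | cut | λ | power, two-sided 0.05 | power, plan's α 0.000437 |
|---|---|---|---|---|---|
| unadjusted | 0.825 | – | 5.19 | 0.62 | 0.10 |
| 0 | 0.825 | 0% | 5.19 | 0.62 | 0.10 |
| 0.2 | 0.785 | 5% | 5.45 | 0.64 | 0.12 |
| 0.3 | 0.735 | 11% | 5.82 | 0.67 | 0.13 |
| 0.5 | 0.575 | 30% | 7.44 | 0.78 | 0.21 |
| 0.8 | 0.185 | 78% | 23.14 | 0.998 | 0.90 |

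A simulation at r = 0.8 (4,000 trials, 214 per arm) agrees: power 0.63 without and 0.997 with the covariate; type I error 0.051 and 0.050.

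**3. The plan's post hoc t-test** (one-tailed, implied α 0.151, taken as one measurement). δ = 0.2 × √(107/(1 − r²)). Unadjusted, δ = 2.069 and power is 0.85, as stated. At r = 0.2, 0.3, 0.5 and 0.8, δ = 2.111, 2.169, 2.389 and 3.448, and power is 0.86, 0.87, 0.91 and 0.99.

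**4. If the site counts in 6.4 are final.** 46 + 106 + 76 + 53 + 2 = 283, so λ = 2.83/variance. With no dropout at two-sided 0.05, power is 0.45 unadjusted, and 0.47, 0.50, 0.60 and 0.97 at the same four values of r.

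**5. With the planned carry-forward.** Simulation of 4,000 trials per case, 278 per arm, with 129/557 = 23% dropping out at random after Visit 2 to Visit 8. At two-sided 0.05, power is about 0.73 unadjusted, and about 0.75, 0.77, 0.86 and above 0.99 adjusted. Type I error is about 0.05 for both. Removal of subjects who become diabetic is not modelled.

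**6. If the eight measurements include baseline as a response.** The main effect is diluted to 7/8: λ = 5.19 × (7/8)² = 3.97, and power at 0.05 is 0.51, below the 0.62 in step 2.

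**Secondary: which term is H01?** The Hypothesis Testing text names neither the main effect nor treatment-by-time. Study medication stops at Month 12, so four of the eight visits are off drug. Under the unadjusted settings of step 2 at 0.05, if half the effect persists off drug (mean d = 0.15, λ = 2.92), main-effect power is 0.40; if none does (mean d = 0.10, λ = 1.30), it is 0.21. Treatment-by-time has λ = Σ(d_t − mean d)² × 107/0.2 on 7 and 2982 df. That is 10.7 and 42.8, with power 0.65 and above 0.99.

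**The case against.** The strongest objection is that the model may already use baseline. The SAP does not say which eight measurements it means. If baseline is one of the eight and H01 is treatment-by-time, then with d = 0 at baseline and 0.2 at the other seven, λ = 0.035 × 107/0.2 = 18.7 and power at 0.05 is 0.91. That possibility stands and the text should settle it. It is not the likelier reading: nine HbA1c and lipid measurements are scheduled against eight in the model, and the sizing run is a one-df main effect. For a main effect, baseline as a response lowers power.

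Other points that stand:

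- The gain depends on an unknown correlation. At 0.2 to 0.3 it is modest. The 0.8 in the SAP is for the repeated measures, and carrying it over to baseline is an assumption.
- If H01 is treatment-by-time, a single baseline coefficient leaves that test unchanged and helps only the contrasts.
- On the plan's own run power is already 0.998, so the gain shows only once subjects are the unit. The two-sided 0.05 is illustrative; the table also gives the plan's α.
- H02, the log-rank comparison of time to diabetes, is unaffected.

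Carry-forward could bring a screening value into the outcome data for someone with no later measurement. That would be imputation, not adjustment.

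**Conclusion.** The concern holds as a recommendation on efficiency; the planned test is not invalid. No section puts the pre-randomisation values into the H01 model as a covariate. For 428 completers at two-sided 0.05, main-effect power rises from 0.62 to between 0.64 and 0.78 for baseline correlations of 0.2 to 0.5, and to 0.998 if the correlation is as high as 0.8. This rests on d = 0.2, a correlation of 0.8 among follow-up visits, a constant baseline correlation, and the main effect as the H01 term. The gain is positive for any non-zero correlation. The missing definition of the H01 term and the contrast intervals is a secondary note, not a demonstrated error. The change should be made; confidence is high.

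**What to change.** Before unblinding, amend Section 6.3 as follows:

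1. Include each outcome's last pre-randomisation value as a covariate in its H01 model: the screening value, or the Visit 1 repeat where labs were redone. Waist is recorded only at screening.
2. State that the eight outcome visits are Months 3 to 24.
3. Take interval contrasts from this adjusted model in place of the independent-samples t-tests, so that the power section and the Post Hoc Tests paragraph agree.
4. Name the H01 test term and define the on-drug (Months 3–12) and off-drug (Months 15–24) contrasts. Whether the on-drug contrast replaces or accompanies the averaged test is the sponsor's design choice.

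Cost: one degree of freedom per model, no new data or visits, and a dated SAP change. The document is dated January 2018 and section 3.6.4 runs the study to April 2018, so the change needs to be made promptly. Item 4 is text only.

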6.2. Sample size estimation/power analysis:

A priori power for H₀₁ was assessed using G*Power Version 3.0.10¹. The results indicate 214 subjects per group with 8 repeated measures for a total sample size of 3424 will achieve a power of approximately 0.99 to detect a small effect size of 0.10 at α = 0.0004.

A priori power for H₀₂ was assessed using the method described by Glantz² to calculate sample size for a two-sample log-rank test to detect differences in the time to event. Based on this design, it will require a minimum of 214 subjects per group to detect a difference between a 17.5% conversion in the Placebo + lifestyle and an 11.5% conversion in the Cinnulin + lifestyle group at α = 0.05 (one-sided) and power of 0.80.

We are enrolling 557 subjects total, for an expected 428 completing the study. We estimate 129 subjects' will either withdraw consent or drop out of the study.

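### The H01 power of 0.99 comes from entering 3,424 measurements as subjects; with the planned 428 subjects, between-group power is about 0.10 at the printed alpha

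*Combined protocol and SAP*

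**What the plan says.** Section 6.2 gives the H01 result in one sentence: "The results indicate 214 subjects per group with 8 repeated measures for a total sample size of 3424" reach power of about 0.99 for f = 0.10 at alpha 0.0004. The SAP in section 6.3 repeats the claim, stating that "214 subjects per group with 8 repeated measures for a total sample size of 3424 will achieve a power of approximately 0.99", and prints the G*Power table behind it. The inputs include "Total sample size = 3424", "Effect size f = 0.1", "Number of groups = 2", 8 repetitions, a correlation of 0.8 among repeated measures and a beta/alpha ratio of 4. The outputs are noncentrality 41.503030, critical F 12.389225, df 1 and 3422, alpha 0.000437447 and power 0.998250.

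The planned number of subjects is stated in section 6.2: "We are enrolling 557 subjects total, for an expected 428 completing the study".

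Under Hypothesis Testing in section 6.3, the analysis of H01 is described as follows: "This hypothesis will be tested by a mixed effects repeated measures analysis of variance (rANOVA"). No significance level is given there for H01.

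Section 6.3 also contains a second power run, for the post hoc t-tests: "214 subjects per group will achieve a power of approximately 0.85 to detect a small effect size of 0.20". That run uses 214 per group and prints df 426.

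**The concern.** A repeated-measures power routine takes the number of subjects as its sample size, and the number of repeats and their correlation as separate inputs. Here the subjects had already been multiplied by 8 before entry. The routine then multiplied by 8 again, as though there were 3,424 x 8 = 27,392 measurements. The printed denominator df of 3422 shows this directly, because 428 subjects in two groups leave 426.

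This is the only power statement for the overall H01 test, which covers glucose, HbA1c, lipids and waist circumference. The SAP opens the post hoc contrasts only if H01 is rejected, so the power of this test also limits what can follow it. Anyone relying on the stated 0.99 could take a null main effect as strong evidence against f = 0.10, which the design cannot give. The post hoc t-test run does not fill the gap. It reaches 0.85 only at a one-sided alpha of 0.15, and at an assumed one-sided 0.05 the same run gives 0.66.

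**Working it through.** **Inputs** (H01 power table in section 6.3, unless noted)

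- f = 0.10; 2 groups; m = 8 repetitions; correlation rho = 0.8; beta/alpha = 4
- N entered = 3424 = 214 x 2 x 8
- N planned = 428 = 214 x 2 (sections 6.2 and 6.3); 557 enrolled (section 6.2)

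**Formula.** For the between-group main effect, lambda = f² x N x m / (1 + (m - 1) x rho), with an F test on 1 and N - 2 df. Here 1 + 7 x 0.8 = 6.6. The printed table does not name the factor tested, but numerator df 1, denominator df N - 2 and the value of lambda all match this test. A time or interaction test would have numerator df 7.

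**Step 1: reproduce the plan.** With N = 3424:

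- lambda = 0.01 x 3424 x 8 / 6.6 = 41.503
- df = 3424 - 2 = 3422
- solving for beta = 4 x alpha gives critical F 12.3892, alpha 0.000437 and power 0.99825

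Every printed output is matched, so both the test and the error are identified.

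**Step 2: enter the planned subjects.** With N = 428:

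- lambda = 0.01 x 428 x 8 / 6.6 = 5.188, one eighth of the printed value
- df = 428 - 2 = 426

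| N | alpha | status of alpha | power |
|---|---|---|---|
| 428 | 0.000437 | printed output | 0.105 |
| 428 | 0.0004 | printed, rounded | 0.100 |
| 428 | 0.077 | compromise rerun, beta/alpha = 4 (critical F 3.147) | 0.693 |
| 428 | 0.05 | assumed | 0.623 |
| 428 | 0.05/7 | assumed | 0.336 |
| 557 (lambda 6.752) | 0.000437 | printed output | 0.176 |
| 557 | 0.05 | assumed | 0.737 |

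**Step 3: what the design can detect.** With 428 subjects, the smallest f with power 0.80 is 0.193 at the printed alpha and 0.123 at an assumed 0.05. Power of 0.99 for f = 0.10 at the printed alpha needs 2,823 subjects, or 2,824 with equal groups.

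**Step 4: sensitivity to the correlation.** With 428 subjects at the printed alpha, power is 0.086 for rho = 0.9, 0.218 for 0.5 and 0.59 for 0.2. It comes close to the stated figure (0.989) only at rho = 0, when repeated measures on one person are treated as independent. The plan states 0.8. Using 9 measures in place of 8 leaves the result at 0.105.

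**The case against.** Four points can be made for the plan.

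- **The alpha of 0.0004 is itself a product of the wrong N.** The run fixed the ratio of beta to alpha and solved for alpha. Correcting only N and keeping the method gives alpha 0.077 and power 0.69, which is arguably the like-for-like comparison. This is fair, and both figures should be shown. However, both sentences state 0.99 at alpha 0.0004 for 214 subjects per group, and that claim has power of about 0.10.
- **H01 is wider than the main effect.** It is tested in a model with treatment and time as fixed effects. By the same G*Power convention, a group-by-time interaction with f = 0.10 and 428 subjects has lambda 0.01 x 428 x 8 / (1 - 0.8) = 171.2 and power near 1, although f has a different meaning there. This stands as a limit on scope: H01 as a whole has not been shown to have 10% power. The plan did not run that test, and it cannot justify the printed figure.
- **The analysis set may be larger than 428.** The protocol specifies intention-to-treat with carry-forward, which points towards all 557 enrolled. Power would still be only 0.18 at the printed alpha and 0.74 at an assumed 0.05.
- **The sample size does not rest on this run.** The H02 log-rank table also prints 428, so correcting H01 does not by itself alter enrolment. That limits the practical effect but leaves the stated power wrong. Nothing here endorses the H02 table. Its 124 events at the mean printed conversion of 14.5% would need about 124 / 0.145 = 855 subjects, a separate matter.

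**Conclusion.** The stated power is wrong as written. The published output reproduces exactly only when 3,424 is taken as the number of subjects, and the plan has 428. On the plan's own f, correlation and number of repeats, between-group power is 0.105 at the printed alpha against a stated 0.998. At no alpha level in the table above does it approach 0.99.

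The conclusion is confined to the between-group main effect, the test that was run. It takes 428 completers as the analysis number and the plan's correlation of 0.8. The levels 0.05 and 0.05/7 are assumptions, since the documents set no alpha for H01. This must be corrected, because a principal design figure contradicts its own inputs in two places.

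**What to change.** Rerun the H01 calculation with a total sample size of 428, 8 repetitions and correlation 0.8, at an H01 alpha that the sponsor chooses and states in section 6.3 before the analysis. Name the effect being tested. Replace the power table and the sentences in sections 6.2 and 6.3, for example with:

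*With 214 subjects per group (428 in total), 8 repeated measures and correlation 0.8, lambda is 5.19 (df 1, 426), and power for the between-group main effect at f = 0.10 is [power] at alpha [level].*

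The power to enter is about 0.10 if the level stays at 0.0004, 0.62 if 0.05 is chosen, or 0.69 at 0.077 if the compromise is rerun. The value 0.077 would again be an output of the chosen ratio and should be labelled so. Delete the total of 3,424 and the power of 0.99.

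The cost is one table, two sentences and one stated alpha. The correction itself requires no added enrolment. The downside is a less favourable stated power.
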